3.1.1 Scheduled study visits

Recruitment of patients will occur during initial contacts with the study coordinator [name] who will present the parents with the opportunity to enroll in the study, and when general information will be given about the study on timeline, procedures involved, tests, costs.

After agreeing in principle to participate in the study, parents and child will be scheduled for **Visit 0**, at which the patients' blood is drawn for testing, questionnaires are completed, the patient is evaluated by the child therapist and is randomized for receiving treatment A (UCB infusion) or B (noninvasive treatment), and the necessary arrangements are made for UCB release from the respective banking site.

Visit 1 is scheduled within 7-14 days from V0, and during this study visit the child will receive either treatment A or B. Treatment B (noninvasive) is administered daily for 6 weeks, and is followed by 2 weeks with no treatment (washout period)

Visit 2 follows at 8 weeks distance from V1, which includes the 2 week washout period after the first treatment is administered. New blood tests are performed, also questionnaires and evaluation by child therapist, and the other treatment in sequence is administered.

Visit 3, Visit 4, and Visit 5 are scheduled at 16, 24 and 52 weeks after first treatment was administered (V1) and involve the neuropsychological evaluation of the child by the therapist and with the 3 questionnaires; brain imaging is recommended at 52 weeks

	Visit 0	V1	V2 (+ 8 weeks)	V3 (+16 wks)	V4 (+24 wks)	V5 (+52 wks)
Labs	CBC, LFTs, Els, HLA; IP	HLA MB	CBC, LFTs, Els, HLA; IP; MB			
Imagis-tics	MRI/CT					MRI/CT
Neuro/Psi Evaluation	M-CHAT-R; Q-CHAT; CAST; - Child therapist	x	M-CHAT-R; Q-CHAT; CAST; - Child therapist	M-CHAT-R; Q-CHAT; CAST; - Child therapist	M-CHAT-R; Q-CHAT; CAST; - Child therapist	M-CHAT-R; Q-CHAT; CAST; - Child therapist
Treatment started	randomi-zation	A/B	B/A	X	X	X

CBC – complete blood count with differential; LFTs – liver function tests, Els – electrolytes; IP – Inflammatory panel – ex ESR, CRP, serum protein electrophoresis, neopterin, IL-6; HLA – Typing of patient HLA- A, HLA-B, HLA-DR; MB - microbiology

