Final Protocol:	June 2019	Clean File:	June 2019
Ethics Approval:	January 2019	Statistical analysis:	
Clinical Phase:		Study Report:	
OBJECTIVES:	To compare the safety and efficacy of administering intravenous autologous cord blood versus personalized noninvasive treatments to children with developmental disorders of the autistic spectrum		
STUDY DESIGN:	An open-label, pilot crossover study over a 12-month period. Participants will be screened and randomized at Visit 0 and at visit V1 will be receiving either intravenous umbilical cord blood or noninvasive treatment. At V2, at 2 months after V1, the other treatment is administered and subsequently the child will be evaluated by questionnaires and child therapist. Parents will report adverse events and complete the M-CHAT, Q-CHAT and CAST questionnaires. Modifications on these questionnaires will be analyzed statistically as a quantitative measure of child's improvement.		
SUBJECTS:	
Inclusion criteria Males and females between 3 and 7 years of age:
 
 • parents informed of the nature of the study and will give written informed consent, • have body weights between 10-30 kg, • have no clinically significant abnormal values on hemoleucogram during screening, • be on no regular medical treatment • have no known allergies to treatments 
Exclusion criteria
 
 • Any genetic or metabolic disease or condition which might compromise the haematopoietic, renal, endocrine, pulmonary, central nervous, cardiovascular, immunological, dermatological, gastrointestinal or any other body system. • History of allergic conditions – asthma, urticaria, eczema. • History of autoimmune disorders 		

	
 • Intake of any medication within 14 days before start of the study • Presence of significant abnormal hemoleucogram results during screening.
TREATMENT TO BE EVALUATED	
Active Treatment A: Autologous umbilical cord blood administered intravenously as single treatment .
 
Active Treatment B: Personalized daily treatment following evaluation with a combination of intranasal Oxytocin; Curcumin; Lecithin, Piracetam, Tecfidera; PQQ; Magnesium citrate and vitamin B6

DURATION OF STUDY	12 months

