3.2.1 Inclusion criteria

To be enrolled, the following criteria have to be fulfilled at Visit 2:

1. Children of either sex between 3 and 7 years.
2. Body weight between 15 and 30 kg
3. Diagnosed with ASD
4. No significant diseases or clinically significant abnormal laboratory values during screening
5. On no regular medical treatment

6. Parents able to be informed of the nature of the study and willing to give written informed consent (Consent must be obtained before any study-related procedures are conducted).

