3.2.4 Criteria for discontinuation

Subjects may be discontinued from study treatment and assessments at any time, at the discretion of the investigator. Specific reasons for discontinuing a subject from the study are:

1. Withdrawal of informed consent.
2. Development of exclusion criteria, pregnancy or other safety reasons during the study.
3. Protocol non-compliance.
4. Incorrect enrollment or randomization of the subject.

For subjects withdrawn from the study, the same measurements and assessments should be performed as done at Visit 5. Adverse events should be followed up and questionnaires completed by parents.

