3.3 Investigational Products and Treatments

3.3.1 Treatment Schedule

Each treatment arm is administered and considered active for a period of maximum 8 weeks; the non-invasive treatment is administered for 6 weeks followed by a 2-week “wash-out” period, and the UCB infusion will be followed by supplement administration after an 8-week interval. Patient evaluation, registration informed consent and randomization occur at initial visit 0 (V0); followed after 14-21 days by V1 (longer for the preparation of UCB infusion), during which the first treatment is administered; V2 after another 8 weeks, at which the second treatment is administered, and V3, V4, and V5, at 16, 24 and 52 weeks respectively after V1.

A tabulated summary of the study visits was given above Section 3.1.1

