4 STUDY MEASUREMENTS AND ENDPOINTS

In this study the following endpoints will be measured/recorded

1. Efficacy - difference in the scores on the questionnaires M-CHAT, Q-CHAT and CAST before and after each treatment

2. Safety – type, severity, duration, treatment and amelioration of each of the adverse effects occurring during respective treatments.

4.1 Primary Safety Endpoints.

–

1. Adverse events (type and frequency)
2. Physical examination parameters (body mass, height, etc)
3. Vital signs: blood pressure, heart rate, respiratory rate, body temperature
4. Laboratory tests
 - HLA testing by genetic sequencing
 - Haematology: CBC - RBC, HB, MCHC, MCH, MCV, RDW, Hct, Hb, WBC Differential count –lymphocytes monocytes, neutrophils, eosinophils, basophils, flowcytometry - CD34+, TNC, viability %
 - Microbiology – presence and sensitivity of pathogens
 - LFTs Serum - Bilirubin (total and conjugated) AST, ALT, GGT, LDH, glucose
 - IP – serum protein electrophoresis, ESR, CRP, fibrinogen
 - Els - sodium, potassium, chloride, calcium, magnesium.

4.2 Measurements at each visit.

See section 3.1.1 for the visit schedule.

Visit 0: Screening Visit

Patients will be examined within 14 days prior to the first ingestion of the investigational products to assess their eligibility to participate. For each child both parents will consent in writing (Appendix 1, Informed Consent Form) to the screening process before the start of the examination. The consent form will also include the study information leaflet.

The examinations and investigations will include:

- Medical history, including history of past use of medications, demographics (date of birth, sex, race) and ASD diagnosis.
- Physical examination including assessment of general appearance, cardiovascular, lungs, mouth, throat and abdomen and measurement of height and body weight. The examination will be made in accordance with the normal clinical routines at the trial center.
- Vital signs: systolic and diastolic blood pressure in supine (after 5 minutes rest) and standing positions (1minute), pulse, respiratory rate and oral temperature.
- Laboratory tests: HLA, Haematology, (see section 4.4.3.2); baseline plasma levels of IP, Els, LFTs (these can be drawn also at V1 if considered by the study PI)

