Based on the results of the testing with the M-CHAT-R, Q-CHAT and CAST questionnaires and the evaluation from child psychologist, a recommendation for treatment will be made for either UCB administration or the noninvasive treatment for 6 weeks

Visit 1: The first treatment is administered

- The pre-dose safety assessments and eligibility checks will be recorded on the relevant pages in the individual CRFs.
- The parents will also be given the 3 questionnaires and instructed on how to complete it.
- The parents will be issued with prescriptions for trial medication, explained how to take the medication and given next appointment date; or
- The UCB infusion is administered

Visit 2: Second Treatment is administered

For these visits the examinations and investigations will include:

- Physical examination (as for visit 1)
- Vital signs: systolic and diastolic blood pressure in supine, pulse, respiratory rate and oral temperature.
- Laboratory tests
 - HLA testing by genetic sequencing
 - Haematology: CBC - RBC, HB, MCHC, MCH, MCV, RDW, Hct, Hb, WBC
 - Differential count –lymphocytes monocytes, neutrophils, eosinophils, basophils,
 - flowcytometry - CD34+, TNC, viability %
 - Microbiology – presence and sensitivity of pathogens
 - LFTs Serum - Bilirubin (total and conjugated) AST, ALT, GGT, LDH, glucose
 - IP – serum protein electrophoresis, ESR, CRP, fibrinogen
 - Els - sodium, potassium, chloride, calcium, magnesium.

Note: For any patient in which any of the above tests indicated levels outside the normal range, a follow-up visit (visit A-C) will be scheduled for an appropriate time (1 or 3 months post visit). All or the above tests will be repeated at this visit.

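### Randomisation takes place at Visit 0, where the screening blood is drawn, and nothing makes allocation wait for the laboratory results that decide eligibility

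*Combined protocol and SAP*

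**What the plan says.** **Timing of randomisation.** The synopsis states "Participants will be screened and randomized at Visit 0". Section 3.1.1 says that at this visit "blood is drawn for testing, questionnaires are completed, the patient is evaluated by the child therapist and is randomized for receiving treatment A" or B, and its visit table also puts randomisation in the V0 column. Section 3.3.1 agrees: "Patient evaluation, registration informed consent and randomization occur at initial visit 0 (V0".

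**Laboratory eligibility.** Section 3.2.1 (item 4) requires "No significant diseases or clinically significant abnormal laboratory values during screening". Section 3.2.2 (item 7) repeats this as an exclusion criterion. The synopsis is narrower and refers only to the hemoleucogram.

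**When eligibility is checked.** Under Visit 1, section 4.2 says "The pre-dose safety assessments and eligibility checks will be recorded on the relevant pages in the individual CRFs". The opening line of section 3.2.1, read literally, requires the inclusion criteria to be met at Visit 2.

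**Blood that may be drawn later.** Under Visit 0, section 4.2 lists "baseline plasma levels of IP, Els, LFTs (these can be drawn also at V1 if considered by the study PI". V1 is the treatment visit: "during this study visit the child will receive either treatment A or B" (section 3.1.1). Section 4.4.2 has blood taken before the first dose of the day.

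**Openness.** Section 3.3.2 describes an open-label study and no procedure for concealing the allocation.

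**The concern.** Eligibility should be settled before allocation, so that whoever decides on a borderline value cannot know which sequence the child has drawn. Here the allocation is made at the visit where the blood is taken. Whether an abnormal value is clinically significant is a matter of judgement, because the plan gives no numerical limits. Someone who already knows whether the child starts with cord blood or with the noninvasive regimen can make that judgement. If the decision leans on that knowledge, even unintentionally, the sequences lose the comparability that randomisation was meant to give.

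The rest of the plan does not repair this. Section 3.2 recruits until at least 25 children have received both treatments, so excluded children are in effect replaced. Section 3.3.2 defines discontinuers and dropouts but no screen failures. The intention-to-treat wording in section 5.2 is spelled out for safety only and does not say how a child found ineligible after randomisation is handled.

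The secondary concern is the safety screen. If liver, electrolyte and inflammatory tests are first drawn at V1, a disqualifying result could be read after treatment. That would work against the aim in section 3.2.3 of keeping risk to patients low.

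**Working it through.** The point rests on the order of procedures, so the sections are set side by side. The plan's one related figure, a minimum of 25 participants, cannot be reproduced because section 5.1 gives no effect size or standard deviation. The point does not depend on it.

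**Order of events**

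1. V0: consent, blood draw, questionnaires, therapist evaluation and randomisation (synopsis; 3.1.1 text and table; 3.3.1). No section inserts a wait for results. By contrast, the study rationale in section 1.2 does make the choice of noninvasive components wait until all tests are done.
2. Interval from V0 to V1: 7 to 14 days in 3.1.1; 14 to 21 days in 3.3.1; at most 14 days, with no minimum, in 4.2. Only a gap of exactly 14 days satisfies all three.
3. V1: eligibility checks recorded, possible draw of inflammatory panel, electrolytes and liver tests, then first treatment (3.1.1, 4.2).
4. V2, 8 weeks after V1: the literal point at which 3.2.1 wants the inclusion criteria met.

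Both points at which the documents place an eligibility check or requirement, V1 and V2, come after the V0 allocation. The V2 one also comes after the first treatment, though it may be a slip of wording.

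**Which tests are concerned**

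- Under the synopsis criterion (hemoleucogram only), the relevant sample stays at V0. The allocation problem remains; the V1 problem does not arise.
- Under 3.2.1 and 3.2.2 (any laboratory value), the tests that may be drawn at V1 count towards eligibility, so both can arise.

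**Scale, under an assumed failure rate f**

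The documents give no value for f; 5% to 15% is an assumption. Expected number failing on laboratory results among n children randomised = n × f:

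- n = 25: 25 × 0.05 = 1.25 and 25 × 0.15 = 3.75, about 1 to 4 children.
- n = 40: 40 × 0.05 = 2 and 40 × 0.15 = 6 children.

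Probability that at least one child fails = 1 − (1 − f)^n:

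- n = 25: 1 − 0.95^25 = 0.72 and 1 − 0.85^25 = 0.98.
- n = 40: 1 − 0.95^40 = 0.87 and 1 − 0.85^40 = 0.998.

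These figures count children exposed to an open exclusion decision. They do not measure bias.

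**The case against.** **Results might be known before allocation at V0.** Section 3.1.1 names randomisation after the blood draw and the evaluations, and the V0 column also holds brain imaging, so V0 may not be one short encounter. The documents do not exclude this. But none requires it, and section 4.4.2 speaks of samples being processed and shipped, so same-day results cannot be presumed.

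**A crossover is less exposed.** Every child is due to receive both treatments and the same criteria apply to both sequences, so uneven filtering bears less directly on the within-child contrast than it would in a parallel trial. This stands. However, V0 to V2 is the only stretch before both treatments have been started, and comparing sequences over it relies on comparable groups.

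**A reader might infer that laboratory eligibility is generally judged after treatment.** The documents do not support that. Section 4.2 calls the V1 checks pre-dose, section 4.4.2 puts the draw before the dose, section 1.2 has the noninvasive components chosen after all tests, and the 3.1.1 table lists these tests at V0 and only HLA and microbiology at V1. The permission in 4.2 may also mean a repeat sample. What remains is a gap: if those tests are deferred and not merely repeated, nothing requires the result before treatment. Laboratory turnaround is not stated.

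**A reader might infer that section 3.2.4 prescribes removal of such children.** It lists "Incorrect enrollment or randomization of the subject" among reasons for discontinuing a subject. That gives a possible route, but no section links it to abnormal laboratory results.

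**Conclusion.** The concern holds for allocation. The synopsis, 3.1.1 and 3.3.1 agree on randomisation at V0, no section makes it wait for laboratory results, and eligibility checks are recorded at V1 in an open-label trial. Exclusions based on laboratory judgement can therefore follow a known sequence. This rests on visit order alone.

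The effect is chiefly on the V0 to V2 comparison between sequences. Its direction and size cannot be derived from the documents. The number of children exposed is unknown; about 1 to 4 per 25 or 2 to 6 per 40 randomised rests wholly on the assumed 5% to 15%. In a trial of this size, that many open exclusions would be material.

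The point about results being read after treatment is secondary. It is confined to the inflammatory panel, electrolytes and liver tests, and it needs three conditions: the broader laboratory criterion of 3.2.1 and 3.2.2 applies, the tests are deferred to V1, and the results come back after treatment.

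**What to change.** 1. In the synopsis, section 3.1.1 (text and table) and section 3.3.1, move randomisation to a step between V0 and V1, carried out only after the V0 laboratory results have been reviewed and eligibility signed off. Record children who fail before this step as screen failures.
2. In section 4.2, state that any V1 samples are repeats and do not establish eligibility.
3. Reconcile with this order the Visit 2 wording in section 3.2.1, the differing laboratory criteria (synopsis against 3.2.1 and 3.2.2) and the three V0 to V1 intervals (3.1.1, 3.3.1, 4.2). The interval finally chosen has to leave time for results, since 4.2 sets no minimum.
4. State that a child excluded on a new finding at the V1 pre-dose check is reported by assigned sequence.

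This removes post-allocation exclusions that rest on V0 laboratory results. It does not bring all post-allocation exclusions to zero, because the V1 check remains.

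The cost is protocol wording, with no added visit or test. The downside is that scheduling of cord-blood release for children who start with treatment A is fixed somewhat later. Preparatory arrangements can still begin at V0, because every child is due to receive cord blood in one period or the other.

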3.2 Study population

This clinical study will include children diagnosed with ASD, 3-7 years, and who meet the inclusion criteria outlined above.

Recruitment will continue until a minimum of 25 patients have received both treatments.

3.2.1 Inclusion criteria

To be enrolled, the following criteria have to be fulfilled at Visit 2:

1. Children of either sex between 3 and 7 years.
2. Body weight between 15 and 30 kg
3. Diagnosed with ASD
4. No significant diseases or clinically significant abnormal laboratory values during screening
5. On no regular medical treatment

6. Parents able to be informed of the nature of the study and willing to give written informed consent (Consent must be obtained before any study-related procedures are conducted).

3.2.2 Exclusion criteria

Any of the following is regarded as a criterion for exclusion from the study:

1. Hypersensitivity or allergic reaction to any drugs or supplements.
2. Any disease or condition which might compromise the haematopoietic, renal, endocrine, pulmonary, central nervous, cardiovascular, immunological, dermatological, gastrointestinal or any other body system.
3. History of allergic conditions – asthma, urticaria, eczema.
4. History or presence of dyspepsia, gastric ulcer or duodenal ulcer.
5. History of autoimmune disorders e.g. systemic lupus erythematosus, haemolytic anemia.
6. Intake of steroid medication within 7 days before start of the study
7. Presence of clinically significant abnormal laboratory results during screening.
8. Participation in a clinical study of any investigational product 1 month prior to visit 1 or during the study.

3.2.3 Justification for inclusion and exclusion criteria

The criteria are set to minimize the risk to the patients, to ensure a study population that will enable the investigation of the set objectives, and to provide equal opportunity for inclusion.

3.2.4 Criteria for discontinuation

Subjects may be discontinued from study treatment and assessments at any time, at the discretion of the investigator. Specific reasons for discontinuing a subject from the study are:

1. Withdrawal of informed consent.
2. Development of exclusion criteria, pregnancy or other safety reasons during the study.
3. Protocol non-compliance.
4. Incorrect enrollment or randomization of the subject.

For subjects withdrawn from the study, the same measurements and assessments should be performed as done at Visit 5. Adverse events should be followed up and questionnaires completed by parents.

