5.2 Statistical analysis

A single statistical analysis will be performed at the end of the study. An intention to treat (ITT) approach will followed, i.e. statistical analysis of safety will be based on data from all patients and from whom meaningful data were collected. Data will be displayed graphically for visual inspection. Descriptive statistics will be presented as means, SEM and ninety percent confidence levels of the means.

Baseline characteristics. The subject disposition will be summarized. Protocol violations will be listed per subject, describing the nature of the violation. Subjects failing to complete the study (as well as the times and reasons for discontinuation) will be displayed. The demographic, background and baseline data will be presented descriptively.

Analysis of Safety. Adverse Events, as reported throughout the course of the trial will be listed individually, per treatment group. Pre-, study and post-study findings of **physical examination, vital sign variables, laboratory variables** (haematology, clinical chemistry and urinalysis), and 12-lead ECG if needed will be listed individually and summarized; values outside the normal range will be listed.

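### Withdrawal rule lets an unblinded investigator end assessments along with treatment, so scheduled scores can be lost selectively; stopping treatment should be separated from stopping assessment

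*Combined protocol and SAP*

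**What the plan says.** Section 3.2.4 treats leaving treatment and leaving assessment as one decision: "Subjects may be discontinued from study treatment and assessments at any time, at the discretion of the investigator". Its list of specific reasons includes "Protocol non-compliance" and "Incorrect enrollment or randomization of the subject". The synopsis and section 3.3.2 describe the study as open-label, so whoever uses this discretion knows which treatment the child is on.

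The same section adds two provisions for children who leave: "For subjects withdrawn from the study, the same measurements and assessments should be performed as done at Visit 5", and "Adverse events should be followed up and questionnaires completed by parents". Neither has a stated date. Nothing says that the V2, V3 and V4 assessments in the section 3.1.1 schedule continue.

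Section 4 defines efficacy as the "difference in the scores on the questionnaires M-CHAT, Q-CHAT and CAST before and after each treatment". Under section 3.1.1 the relevant scores fall at V0, at V2 (8 weeks) and at V3 (16 weeks), with later follow-up at V4 and V5.

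Section 5.2 says "An intention to treat (ITT) approach will followed" and explains it as: "statistical analysis of safety will be based on data from all patients and from whom meaningful data were collected". It names no efficacy population and no rule for missing scores. Section 3.3.2 only labels withdrawn children as dropouts. Section 3.2 keeps recruiting until at least 25 children have been given both treatments.

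**The concern.** An intention-to-treat comparison needs outcomes from randomised children whether or not they complied and whether or not an allocation error occurred. A rule that lets the investigator take exactly those children off the visit schedule works against that. What remains for them, one assessment set and parent questionnaires at unspecified times, need not line up with the 8-week and 16-week scores from which the before/after differences are formed.

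The loss is unlikely to be random. Treatment A is a single infusion and treatment B is taken daily for 6 weeks with a diary of intake, so missed dosing is more likely on B. The sequence matters too. A child removed during B who was allocated B first never reaches A, so the within-child comparison goes as well. At stake is whether the A-versus-B comparison describes the children randomised or only those whom an unblinded investigator kept.

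**Working it through.** **Step 1. What happens to a child removed during B, by sequence** (sections 3.1.1, 3.2 and 3.2.4).

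| Sequence | Scheduled score after A | Scheduled score after B | Counts towards the 25? |
|---|---|---|---|
| A then B | V2, already collected | V3, not promised | Yes on a plain reading, because both treatments were started; not replaced |
| B then A | V3, never reached | V2, not promised | No; recruitment continues and another child takes the place |

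The second row restores the number but substitutes a child who stayed for one who did not. That is selection. The first row can cost a pair.

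**Step 2. The plan's own figure.** Section 5.1 gives 25 participants, alpha 0.05 and 80% power, with no effect size, SD, sidedness or dropout rate, so 25 cannot be reproduced. It can only be solved backwards. For a two-sided paired comparison the normal formula gives d = (1.960 + 0.842)/√25 = 0.560. The noncentral t with 24 degrees of freedom gives d = 0.584. The second value is used below.

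**Step 3. Selection (loss rates and gaps are assumptions).** Let a share q of children be removed, and let their A-minus-B difference lie g SDs from that of the children kept, in SDs of the within-child difference. If the true mean over all randomised children is zero, the children kept have mean q × g. For example, q = 0.2 and g = 1.0 give a shift of 0.20 SD. A paired t-test on n = 25(1 − q) children, rounded, has noncentrality q·g·√n, here 0.20 × √20 = 0.894, and rejects as follows.

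| Removed | n | g = 0.5 | g = 1.0 |
|---|---|---|---|
| 10% | 22 | 5.6% | 7.3% |
| 20% | 20 | 7.1% | 13.6% |
| 30% | 18 | 9.2% | 22.5% |

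Topping up does not help. With the same shift and n held at 25, the 20%, g = 1.0 case has noncentrality 0.20 × 5 = 1.0 and rejects 16.1% of the time. A larger sample estimates the shifted mean more precisely.

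**Step 4. Power, only where losses are not replaced.** With d fixed at 0.584, power is 80% at n = 25, 78.2% at 24, 76.3% at 23, 74.3% at 22 and 69.8% at 20. With the synopsis optimum of 40 enrolled and 30% lost, 28 remain and power is 84.6%.

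**The case against.** The strongest reply is that section 3.2.4 does not abandon these children. It requires an assessment set, adverse-event follow-up and parent questionnaires, and the three efficacy instruments are parent questionnaires. This stands in part: outcome data are not wholly lost. A reader might infer that the exit set is taken on the day of withdrawal and that nothing follows, but the section does not say so. The supportable criticism is that the timing is unstated and the scheduled visits are not kept.

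Second, a reader might infer a flat contradiction with intention-to-treat. Section 5.2 explains that term only for safety, and only for patients with meaningful data, and adverse events are followed after withdrawal. So this is an inconsistency together with a gap: efficacy has no defined population.

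Third, a reader might infer that the losses fall only on B. The listed reason is protocol non-compliance, which is wider than missed doses: the diary runs throughout the study, incidental medication must be recorded (section 3.3.5), and joining another trial is barred (section 3.2.2). Incorrect enrolment or randomisation is not tied to either treatment. That B is more exposed is a reasonable inference from the design, but no rates are given.

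Fourth, a reader might take a power loss as the headline, or say that the B effect is overstated by 11% to 25%, from 1/(1 − p) with p = 0.1 and 0.2. The recruitment rule replaces some losses, so the power figures are an upper bound on the harm. The 11% to 25% assumes that every non-complier gains nothing, that all are removed, and that no exit score is used. It also concerns B alone, whereas the primary objective is A against B.

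**Conclusion.** The point holds as an avoidable route to selection bias. The rule joins two decisions that should be separate, gives both to an unblinded investigator, and does not secure the scheduled scores that the efficacy endpoint needs. It does not fit the intention-to-treat approach the plan names.

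Its size cannot be taken from the documents. Under assumed removal of 10% to 20% and a gap of 0.5 to 1 SD between removed and kept children, the nominal 5% error becomes 5.6% to 13.6%; if the removed children do not differ, there is no such bias. The direction for A against B is not established. Lost power is secondary: 76.3% at n=23 or 69.8% at n=20, for assumed unreplaced losses and a back-solved d of 0.584. The change is worth making because it is cheap and scores not collected on schedule cannot be recovered at analysis.

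**What to change.** In section 3.2.4, write separate rules for stopping treatment and stopping assessment. After non-compliance, stopped treatment, or incorrect enrolment or randomisation, continue the three questionnaires and the therapist evaluation at the scheduled V2 to V5 visits unless consent is withdrawn. When treatment stops, and any safety reason that makes assessments inappropriate, remain for the clinicians. Where assessments do end, state when the exit set and the parent questionnaires are due.

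In section 5.2, define the efficacy population as all randomised children, analysed in the sequence allocated, and say how missing scores are handled. Reconcile this with section 3.2, stating whether a child who starts the second treatment but has no score after it counts towards the 25.

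The cost is protocol wording and a small extra burden of visits and questionnaires for a few families.
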